Description of change	The data from each module will be analysed and reviewed together with the data from other studies in the same combination project to evaluate the safety and efficacy benefit in explored indications/patient populations. Decisions on further development will be made based on an analysis of the aggregated data for each combination via a meta-analytic approach implementing quantitative Go-NoGo rules. Results of the meta-analytic approach will be summarised as an internal research report and will be used to support the rationale and the benefit-risk assessment for future development trials, if applicable.
Rationale for change	The text clarifies how the data from each module will contribute to the overall development plan for each potential combination and how the data from each module will be used going forward.
Section to be changed	10.2 MANAGEMENT OF IMMUNE-RELATED ADVERSE EVENTS
Description of change	In the event of an infusion-related reaction \leq Grade 2, treat the symptoms accordingly with antihistamine or corticosteroids if needed, the infusion rate of study drug(s) may be decreased by 50% or interrupted until resolution of the event and re-initiated at 50% of the initial rate until completion of the infusion. In patients experiencing infusion-related reactions \leq Grade 2, subsequent infusions may be administered at 50% of the initial rate. If an infusion-related reaction is Grade 3 or higher in severity at any point during the study, permanently discontinue study drug(s).
Rationale for change	More detail has been provided on what to do in the event of an infusion related reaction.

11.2 GLOBAL AMENDMENT 2

Number of Amendment	2
Date of amendment	14 JUL 2021
EudraCT number EU number	2018-002344-81

BI Trial number	BI 1381-0009
BI Investigational Medicinal Product(s)	See Modules
Title of protocol	An open-label, Phase II, platform trial evaluating safety and efficacy of multiple BI 754091 anti-PD-1 based combination regimens in PD-(L)1 naïve and PD-(L)1 pretreated patient populations with advanced and/or metastatic solid tumours who have had at least one line of systemic therapy
To be implemented only after approval of the IRB / IEC / Competent Authorities	X 
To be implemented immediately in order to eliminate hazard – IRB / IEC / Competent Authority to be notified of change with request for approval	
Can be implemented without IRB / IEC / Competent Authority approval as changes involve logistical or administrative aspects only	
Section to be changed	Title page/ BI IMP(s)
Description of change	Added ezabenlimab
Rationale for change	BI 754091's INN is "ezabenlimab". The section was updated to show the new name associated with BI 754091
Section to be changed	Coordinating Investigator
Description of change	[REDACTED]
Rationale for change	[REDACTED] will replace [REDACTED] as the coordinating investigator.
Section to be changed	Synopsis Main Inclusion and Exclusion Criteria and Section 3.3.2 Inclusion Criteria
Description of change	5 Eastern Cooperative Oncology Group (ECOG) score: 0 to or 1.
Rationale for change	To clarify that patients with either an ECOG of 0 or 1 may be enrolled onto the study.

Section to be changed	Synopsis Main Inclusion and Exclusion Criteria and Section 3.3.2 Inclusion Criteria and Section 3.3.3 Exclusion Criteria
Description of changethe Investigator's and/or Medical Monitor's....
Rationale for change	To clarify that the Medical Monitor plays a role in determining if a patient meets the enrollment criteria.
Section to be changed	Synopsis Main Inclusion and Exclusion Criteria and Section 3.3.3 Exclusion Criteria
Description of change	12. Known presence of symptomatic central nervous system (CNS) metastases, unless treated and asymptomatic and off corticosteroids and anti-convulsant therapy for at least 2 weeks prior start of treatment.
Rationale for change	To clarify that known, untreated, asymptomatic CNS metastases will also be an exclusion criteria.
Section to be changed	Section 3.3.2 Inclusion Criteria
Description of change	6 Patient must agree to a pre-treatment biopsy (if archival tissue is not available) and on-treatment tumour biopsy. If archived tumour tissue is available from the last treatment failure, sections may be supplied instead of a pre-treatment biopsy. If the patient does not have archival tumour tissue and is not biopsiable because of a safety concern the patient could be considered for study after discussion with the Medical Monitor to potentially allow for inclusion of a patient with for a tumour type of interest.
Rationale for change	To prevent the enrollment of ineligible patients.
Section to be changed	Section 3.3.3 Exclusion Criteria
Description of change	5. Active infection requiring systemic treatment (antibacterial, antiviral, or antifungal therapy) at start of treatment in this trial. Patients may be enrolled onto the study following an 7-day washout period after the end of systemic treatment for active infection.
Rationale for change	To clarify how soon after an active infection a patient would be allowed to enrol.

11.3 GLOBAL AMENDMENT 3

Date of amendment	12 JUN 2023
EudraCT number	2018-002344-81
EU number	
BI Trial number	1381-0009
BI Investigational Medicinal Product(s)	See Modules

Title of protocol	An open-label, Phase II, platform trial evaluating safety and efficacy of multiple ezabenlimab anti-PD-1 based combination regimens in PD-(L)1 naïve and PD-(L)1 pretreated patient populations with advanced and/or metastatic solid tumours who have had at least one line of systemic therapy
To be implemented only after approval of the IRB / IEC / Competent Authorities	
To be implemented immediately in order to eliminate hazard – IRB / IEC / Competent Authority to be notified of change with request for approval	
Can be implemented without IRB / IEC / Competent Authority approval as changes involve logistical or administrative aspects only	
Section to be changed	Title Page/Clinical Trial Leader
Description of change	Trial Clinical Monitor [REDACTED] Phone: [REDACTED] [REDACTED] Phone: [REDACTED]
Rationale for change	Role of 'Trial Clinical Monitor' changed to 'Clinical Trial Leader' due to update in role title within BI; role changed over to [REDACTED].
Section to be changed	Title Page/Coordinating Investigator and Synopsis
Description of change	[REDACTED] [REDACTED] Phone: [REDACTED]

Rationale for change		Updated company name.
Section to be changed		Title page and throughout the document
Description of change		BI 754091 was changed to its INN, 'ezabenlimab'.
Rationale for change		Change was communicated with Global Amendment 2 (14 Jul 2021) but was not introduced to the study title or replaced throughout the document.
Section to be changed		Throughout the document
Description of change		[REDACTED] updated to [REDACTED]
Rationale for change		Updated to legal name.
Section to be changed		Section 4.1 Investigational Treatments

2. LIST OF ABBREVIATIONS

Term	Definition / description
AE	Adverse Event
BHM	Bayesian Hierarchical Model
CR	Complete Response
CTP	Clinical Trial Protocol
CTR	Clinical Trial Report
DC	Disease Control
DoR	Duration of Response
ICH	International Conference on Harmonisation
IPD	Important Protocol Diviations
MedDRA	Medical Dictionary for Regulatory Activities
MQRM	Medical Quality Review Meeting
MTD	Maximum Tolerated Dose
OR	Objective Response
OS	Overall Survival
PD	Progression of Disease
PFS	Progression-Free Survival
PK	Pharmacokinetics
PR	Partial Response
PSTAT	Project Statistician
PT	Preferred Term
RECIST	Response Evaluation Criteria in Solid Tumours
REP	Residual Effect Period
SA	Statistical Analysis
SAE	Serious Adverse Event
SD	Stable Disease
SOC	System Organ Class
ToC	Table of Contents
TS	Treated Set
TSAP	Trial Statistical Analysis Plan

3. INTRODUCTION

As per ICH E9 [\[1\]](#), the purpose of this document is to provide a more technical and detailed elaboration of the principal features of the analysis described in the protocol, and to include detailed procedures for executing the statistical analysis of the primary and secondary variables and other data.

This TSAP assumes familiarity with the Master and Module C Clinical Trial Protocol (CTP), including Protocol Amendments. In particular, the Module C TSAP is based on the planned analysis specification as written in Master and Module C CTP Section 7 “Statistical Methods and Determination of Sample Size”. Therefore, Module C TSAP readers may consult the Master and Module C CTP for more background information on the study, e.g., on study objectives, study design and population, treatments, definition of measurements and variables, planning of sample size, randomization.

SAS® Version 9.4 or the latest version will be used for analyses.

R v3.5.1 and JAGS v4.3.0 or the latest versions will be used for BHM analysis.

4. CHANGES IN THE PLANNED ANALYSIS OF THE STUDY

Refer to the Master TSAP.

5. ENDPOINT(S)

5.1 PRIMARY ENDPOINT(S)

Refer to the Master TSAP.

5.2 SECONDARY ENDPOINT(S)

5.2.1 Key secondary endpoint(s)

This section is not applicable because no key secondary endpoints have been defined in the CTP.

5.2.2 Secondary endpoint(s)

[figure not shown]
[figure not shown]
Refer to the Master TSAP.

5.3 FURTHER ENDPOINT(S)

Refer to the Master TSAP.

5.4.1 Demographics and baseline characteristics

Refer to the Master TSAP.

[figure not shown]

Boehringer Ingelheim
TSAP for BI Trial No: 1381.9

Proprietary confidential information © 2022 Boehringer Ingelheim International GmbH or one or more of its affiliated companies

c39700100-01

Page 9 of 22

6. GENERAL ANALYSIS DEFINITIONS

6.1 TREATMENT(S)

Patients in this Module of the clinical trial will receive BI 836880 combined with BI 754091 by i.v. infusion after signing the Master and Module C informed consent forms and completing the screening processes. Treatment will be administered every 3 weeks (1 cycle = 21 days).

For definition of treatment periods refer to the Master TSAP.

6.2 IMPORTANT PROTOCOL DEVIATIONS

Refer to master TSAP for definition of iPD criteria listed in Table 6.2: 1.
The module C specific iPD criteria are listed in [Table 6.2: 1](#) below.

Table 6.2: 1 Module C Important protocol deviations

Category / Code	Description	Comment / Example	Excluded from	Automatic/ Manual
A	Entrance criteria not met			
A1a	Inclusion criteria not met			
A1a.1	No measurable lesions according to RECIST 1.1	Inclusion criterion (IN) 3 not met	None	Automatic
A2a	Exclusion criteria met			
A2a.1	Unresolved toxicity from previous treatment.	Exclusion criterion (EX) 2 met	None	Automatic
A2a.2	Significant cardiovascular/ cerebrovascular disease.	Exclusion criterion (EX) 3 met	None	Automatic
A2a.3	Severe haemorrhagic or thromboembolic event in past 12 months	Exclusion criterion (EX) 4 met	None	Automatic
A2a.4	Known inherited predisposition to bleeding or to thrombosis	Exclusion criterion (EX) 5 met	None	Automatic
A2a.5	Patients who require full-dose anticoagulation	Exclusion criterion (EX) 6 met	None	Automatic
A2a.6	Prior anti-angiogenic therapy (with the exception of CRC Cohort)	Exclusion criterion (EX) 7 met	None	Automatic

6.3 SUBJECT SETS ANALYSED

Module C Screened Set:

[figure not shown]
This patient set includes all patients who have signed the informed consent for the study and module C. The screened set will be used for patient disposition tables.

Module C Treated Set (TS):

This patient set includes all patients who were documented to have received at least one dose of trial medications in Module C. The TS is used for both efficacy analysis and safety analyses.

Module C Pharmacokinetic Set (PKS):

This patient set includes all patients in the TS with at least one valid plasma concentration. PKS will be used for all pharmacokinetic analyses.

6.5 POOLING OF CENTRES

This section is not applicable because centre/country is not included in the statistical analyses.

6.6 HANDLING OF MISSING DATA AND OUTLIERS

Refer to the Master TSAP.

6.7 BASELINE, TIME WINDOWS AND CALCULATED VISITS

Baseline values will be the measurements taken most recently prior to first administration of study drug in Module C.

Study day will be calculated relative to the date of the first administration of study drug in Module C. The day prior to first administration of study drug will be 'Day -1' and the day of first administration of study drug will be 'Day 1'; therefore 'Day 0' will not exist.

In order to identify whether consecutive imaging time points are missing for a given patient in this module, a nominal time point (i.e. Week 6, 12, 18 ... etc.) will be assigned to each and every image. This is achieved by creating windows for every radiological response assessment. These windows are defined in [Table 6.7: 1](#).

Table 6.7: 1 Nominal time points and windows for imaging

Nominal time point (weeks from start of study drug)	Due date of scans (days)*	Window (days)
6	43	1 to \leq 64
12	85	65 to \leq 106
18	127	107 to \leq 148
24	169	149 to \leq 200
33	232	201 to \leq 263
42	295	264 to \leq 326
51	358	327 to \leq 389
Etc., 9-week interval	Etc.	Etc.

* The date of the first dose of study medication is Day 1

If a patient does not have an image in one of the windows described above, he/she will be said to have missed an assessment for that time point.

Table 6.7: 2 Time windows for assignment of safety lab measurements to visits for statistical analysis

Window No.	Nominal visit	Nominal day	Interval
0	Cycle 1	1	NA
1	Cycle 1	8	[2,11]
2	Cycle 1	15	[12,18]
3	Cycle 2	22	[19,32]
4	Cycle 3	43	[33,53]
n+1	Cycle n	$21*(n-1)+1$	$[21*(n-1)-9, 21*(n-1)+11]$
18	EOT	$21*16+1$	[327, 351]
19	Safety Follow up	$21*16+31$	$[352, \infty]$

Note: n=3,4,5,...,16.

For patients discontinuing treatment before Cycle 16 or receive treatment beyond Cycle 16, identify the last treatment cycle n (≥ 3) and time windows of EOT and Safety Follow up will be derived according to [Table 6.7: 3](#).

Table 6.7: 3 Time windows for patients discontinuing treatment before Cycle 16 or receive treatment beyond Cycle 16

Window No.	Nominal visit	Nominal day	Interval
n+1	Cycle n	$21*(n-1)+1$	[$21*(n-1)-9$, $21*(n-1)+11$]
n+2	EOT	$21*n+1$	[$21*n-9$, $21*n+15$]
n+3	Safety Follow up	$21*n+31$	[$21*n+16, \infty$]

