4. TREATMENTS

4.1 INVESTIGATIONAL TREATMENTS

This is an open-label study. Specific dosing and treatment regimens for each of the ezabenlimab combinations are described in the individual Modules. Selection of the treatment-specific Module will be determined by the patient's tumour type, prior treatment, and algorithm (such as Interactive Response Technology [IRT]) for patient assignment. Patients will sign a Master ICF prior to any Master screening procedures and will sign the Module ICF prior to the occurrence of any Module-specific procedures.

For agents to be combined with ezabenlimab, selection of doses, method of assignment to treatment, any dose modification instructions, drug administration, and drug accountability are described in the respective Modules of this clinical protocol.

Dose reductions or escalations of ezabenlimab are not permitted. Treatment administration may be delayed to manage AEs by one cycle, plus an additional 3 weeks, following discussion with the Medical Monitor.

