4.3 TREATMENT COMPLIANCE

Study drug will be administered at the sites by the Investigator and/or trained site personnel, and dosing will be recorded in the eCRF. Therefore, actual dosing is expected to precisely follow the prescribed drug regimen in the applicable Module. Missed or interrupted doses will be recorded in the eCRF with the associated reasons. The method of collecting dosing information assures that total exposure can be calculated programmatically taking into account any missing doses.

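### The SAP places the safety-lab EOT and Safety Follow up windows by last cycle number, not last-dose date, so dosing delays of 11 days or more can mislabel labs; last cycles 1 and 2 have no usable windows

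*SAP*

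**What the plan says.** SAP 6.7 fixes the time origin: "Study day will be calculated relative to the date of the first administration of study drug in Module C". Table 6.7: 2, headed "Time windows for assignment of safety lab measurements to visits for statistical analysis", then assigns labs to visits by study day. From Cycle 3 on, the Cycle n window is 10 days either side of nominal Day 21(n-1)+1. For a 16-cycle course, EOT is Days 327 to 351 and Safety Follow up starts on Day 352.

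For patients who stop before Cycle 16 or go beyond it, the SAP says to "identify the last treatment cycle n", restricted to n of at least 3, and that "time windows of EOT and Safety Follow up will be derived according to" Table 6.7: 3. That table gives EOT as Days 21n-9 to 21n+15 (nominal Day 21n+1) and Safety Follow up from Day 21n+16 (nominal Day 21n+31). The SAP does not say how cycles are numbered after a hold.

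SAP 6.1 sets a 21-day cycle. On delays, Master protocol 4.1 states: "Treatment administration may be delayed to manage AEs by one cycle, plus an additional 3 weeks, following discussion with the Medical Monitor". Under Master protocol 4.3, "Missed or interrupted doses will be recorded in the eCRF with the associated reasons", so the dose dates needed for another rule should be in the database.

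**The concern.** EOT and Safety Follow up describe a patient's position relative to stopping treatment, yet the windows are placed by a schedule that assumes every cycle began on time. A held dose moves the real last dose later while the windows stay where they were. A lab drawn on a dosing day can then be tabulated as an end-of-treatment or follow-up value, and a real EOT lab can move into follow-up. Delays are permitted in order to manage adverse events, so the patients affected include some whose labs are of particular interest.

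The limit to n of at least 3 leaves a second gap. The first scan is due on Day 43 (Table 6.7: 1), which is also nominal Cycle 3 Day 1. A patient taken off treatment at that scan before being dosed has a last cycle of 2, and neither table gives that patient a usable EOT or follow-up window.

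**Working it through.** **Inputs.** Cycle length is 21 days (SAP 6.1). The window formulas come from Tables 6.7: 2 and 6.7: 3. The permitted delay is one cycle plus 3 weeks (Master protocol 4.1), which is 21 + 21 = 42 days.

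**Reproducing the SAP's figures.** With n = 3, the Cycle n window is 21×2-9 = 33 to 21×2+11 = 53. With n = 16, EOT is 21×16-9 = 327 to 21×16+15 = 351, and follow-up starts on Day 352. All agree with Table 6.7: 2, so the two tables use the same rule.

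**Windows relative to the scheduled last dose.** The scheduled last dose is on Day 21(n-1)+1 = 21n-20. Relative to that day, the Cycle n window ends at +10 (Day 21n-10), EOT runs from +11 (Day 21n-9) to +35 (Day 21n+15), and follow-up starts at +36 (Day 21n+16). Because n cancels, the thresholds below hold for every n of at least 3.

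**Cumulative delay d, with n the last cycle actually given.**
- The last cycle's Day 1 lab falls on Day 21n-20+d. It is labelled Cycle n for d up to 10, EOT for d of 11 to 35, and Safety Follow up from d = 36.
- A lab 21 days after last dose (the table's nominal EOT interval) falls on Day 21n+1+d. It leaves the EOT window when 21n+1+d exceeds 21n+15, that is, from d = 15.

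Example with n = 6 (Cycle 6 Days 96-116, EOT 117-141, Safety Follow up from 142):

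| Delay (days) | Last Day 1 lab | Label | Lab 21 days later | Label |
|---|---|---|---|---|
| 0 | Day 106 | Cycle 6 | Day 127 | EOT |
| 10 | Day 116 | Cycle 6 | Day 137 | EOT |
| 11 | Day 117 | EOT | Day 138 | EOT |
| 15 | Day 121 | EOT | Day 142 | Safety Follow up |
| 36 | Day 142 | Safety Follow up | Day 163 | Safety Follow up |
| 42 | Day 148 | Safety Follow up | Day 169 | Safety Follow up |

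Two separate 7-day delays (d = 14) put Cycle 6 Day 1 on Day 120, which is labelled EOT.

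**Other ways of numbering n.**
- *Each fully skipped 21-day cycle advances n.* Only the remainder after whole cycles matters. The Day 1 lab is still labelled EOT for d of 11-20 and 32-41, but not for d = 21 or 42.
- *n is the calendar cycle window that contains the last dose.* The last dose then lies, by construction, between Days 21(n-1)-9 and 21(n-1)+11. A lab 21 days later lies between Days 21n-9 and 21n+11, inside EOT. A lab at the nominal follow-up interval of 51 days lies between Days 21n+21 and 21n+41, inside Safety Follow up. None of these labs is mislabelled.

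**Last cycle 1 or 2.** Table 6.7: 3 excludes both, and the fixed EOT window in Table 6.7: 2 (Days 327-351) cannot describe an early stopper. Extending the formula to n = 2 gives EOT Days 33-57, which does not collide with Cycle 2 (Days 19-32). Extending it to n = 1 gives EOT Days 12-36, which overlaps the Cycle 1 Day 15 window (Days 12-18).

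**The case against.** The strongest reply is that n is undefined and the section concerns calculated visits. On that view n could be the calendar window containing the last dose, and the mislabelling disappears. A last dose on Day 117, for instance, would fall in the Cycle 7 window, giving n = 7 and the label Cycle 7. The text does not exclude this, so the error is conditional on how n is read. But the SAP does not state that reading. The last treatment cycle would more naturally be taken as the last one given, and two programmers could reasonably produce different tables.

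A second reply is that no affected output can be seen. SAP 7.8.2 leaves laboratory analysis to the Master TSAP, and Master protocol 7.3.4 describes reference-range and distribution summaries without saying that they are by visit. That stands as a limit on the consequence. Likewise, the 15-day threshold assumes an EOT lab exactly 21 days after last dose, and Master protocol 4.1 says that for combination agents "any dose modification instructions, drug administration, and drug accountability are described in the respective Modules of this clinical protocol". The Module C protocol was not available and may set other timing.

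A reader might infer that every cycle window should be re-anchored to actual dose dates. The material does not support going that far. The present windows are contiguous, and full re-anchoring with the same widths would leave 21 study days outside every window after a 21-day hold (14 if the hold is before Cycle 2). Labs taken while an adverse event is being managed would then drop out of the by-visit tables.

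**Conclusion.** The point holds, as a minor one. With n read as the last cycle given, the stated rule puts wrong visit labels on last-cycle Day 1 labs from a cumulative delay of 11 days, and on nominally timed EOT labs from 15 days. Both are within the 42 days that Master protocol 4.1 allows. Delays of up to 10 days are absorbed. Separately, last cycles 1 and 2 have no usable EOT or follow-up windows; taken alone, that would be missing detail.

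The conclusion rests on that reading of n, on 21-day cycles, and on by-visit lab summaries actually using these windows, which could not be confirmed without the Master TSAP.

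A reader might also infer that the safety conclusions are biased. The documents do not support that. On-treatment status of adverse events is set by the residual effect period (Master protocol 5.2.6.2.1 and 7.3.4), not by these windows, and efficacy does not use them. Nothing in the documents gives the frequency of delays or a direction of bias, and the trial is descriptive (Master protocol 7.2).

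**What to change.** Keep the calendar cycle windows and anchor only the last two windows to the actual last dose. Let L be the study day of the last dose of any Module C study drug:
- EOT: Days L+11 to L+35.
- Safety Follow up: from Day L+36.
- Labs up to Day L+10 keep their calendar cycle window, with the Table 6.7 cycle formula continued as far as needed.
- Apply this for every last cycle. If the only dose is on Day 1, start EOT on Day 19, after the Cycle 1 Day 15 window: EOT Days 19-36, follow-up from Day 37. An on-schedule last cycle of 2 (L = 22) gives EOT Days 33-57 and follow-up from Day 58.

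For on-schedule patients L = 21n-20, so L+11 = 21n-9, L+35 = 21n+15 and L+36 = 21n+16. Labels match the present tables on every study day, and no gaps open. In the n = 6 example with an 11-day delay, L = 117: the dosing-day lab keeps a cycle label, EOT is Days 128-152, and follow-up starts on Day 153. Naming the last dose of any study drug settles the case where the two agents stop on different dates.

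The cost is SAP wording and minor programming, with no new data. After a delay, on-treatment labs still carry calendar cycle labels (Day 117 in the example is labelled Cycle 7). A lab drawn more than 35 days after last dose is still labelled follow-up, as it is now for an on-schedule patient.
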